1.3 Exclusion/removal criteria

- 1) The patient voluntarily withdrew the informed consent
- 2) the operation was cancelled

2. Grouping of study participants:

This study planned to implement simple randomization with SAS: Group 1 was the group using the new oropharyngeal airway (experimental group);The other group was the control group (control group).

3. Blinded/unblinded patients This study was an open trial, and no blinded method was used.

4. Remedial and supportive treatment (necessary treatment measures for the occurrence of SAE related to the study)

(1) Continue to inject propofol with a range of 5ml to achieve the appropriate depth of anesthesia again if coughing, limb struggle and other conditions occur during the procedure;

(2) If severe airway spasm, obstruction of ventilation occur during the operation, and the airway cannot be effectively improved, measures such as mask pressure oxygen, emergency tracheal intubation or cricothyroid puncture should be taken. In the event of intraoperative emergencies and accidents, patients should be treated primarily, and patients should be put in the first place in accordance with clinical routine rescue and treatment of study participants.

5. Study Participant Early withdrawal/Trial termination criteria: Unconditional termination of the trial at any time when a study participant proposes to withdraw from the trial, while still guaranteeing patient safety throughout the process.

Research program

1. Study Participant Management

1) Study participant recruitment methods: The staff participating in this clinical trial was responsible for recruitment under the control of the principal investigator. 130 patients with obstructive sleep apnea hypopnea syndrome (diagnosed as OSAHS by polysomnography monitoring) who met the enrollment criteria and intended to undergo painless gastrocolonoscopy in our hospital were initially screened, and the recruitment materials were distributed to the study participants and their families.

2) Informed consent process: When enlisting study participants, inform study participants and their families of the detailed contents of the study, possible risks and benefits (see informed consent for details) in accordance with the content and requirements of informed consent, obtain consent from study participants and their families, and sign informed consent before anesthesia induction.

- 3) Check the admission criteria: Participants were selected strictly according to the admission and exclusion criteria, and should be checked before entering the operating room and before anesthesia induction.
2. Safety evaluation procedure: Study participants with oropharyngeal tumor, inflammation, infection, ulcer and other bleeding risk withdrew from the test, and ventilation should not be used.
3. Termination and withdrawal procedures: Study participants with severe airway spasm, obstruction of ventilation, or failure to effectively improve airway, requiring emergency tracheal intubation or cricothyroid puncture, should immediately take life-saving measures and automatically withdraw from the study.
4. This study was conducted in collaboration with the Department of Anesthesia and Perioperative Medicine, the Department of Digestive endoscopy, and the Sleep Disorder Diagnosis and Treatment Center of Neurology. In the stages of study participant recruitment and trial conduct, tasks are allocated according to the professional background and skills of each team member to ensure that everyone's responsibilities are clear and they can work together.

The beginning and end of the experiment

Start: Trial is expected to begin after ethical review in July-August 2024.

End: Clinical trial phase is expected to end in May-June 2025.

Clinical criteria for early termination of trials

Criteria for termination: The study should be terminated if participants had severe airway spasm, obstruction of ventilation, or inability to effectively improve airway, or if emergency tracheal intubation or cricothyroid puncture were required. Or withdrawal of informed consent by study participants requires termination of the trial.

Data security and monitoring Programme

1. Overview of data Management methods Original records refer to all kinds of data, text, charts, pictures and other original materials directly recorded or statistically formed by means of experiment, observation, investigation or data analysis in the process of clinical and scientific research. The original record is the direct record of the original data obtained in the process of scientific experiment, which can be used as the important basic data for in-depth research in different periods. The original test records should be able to reflect the most real and original conditions in the test, and

must be timely, true, accurate and complete, prevent omission and random alteration, and prohibit forgery and fabrication of data. The original test data and materials should be retained for at least 10 years after the complete end of the test.

2. Reporting and collection of adverse events and serious adverse events An adverse event is any adverse symptoms and abnormal signs that occur after the application of an intervention, whether or not the trial has a causal relationship. Any adverse events, including those voluntarily provided by study participants or queried by investigators or detected by monitoring, should be recorded on the CRF and actively managed and followed up closely until remission or stabilization. All adverse events must be tracked, and the case report form should be filled in by the investigator in time to ensure that the content is accurate and the summary is timely. CRF form should not be altered in general, if there are errors that need to be modified, you should sign the amendment and sign the amendment date. Adverse event reports should include: adverse event content (symptoms, signs, abnormal indicators), start and end dates, evaluation of adverse event severity (mild, moderate, alarming), action taken (no action, stop intervention, treatment), adverse event outcome (no adverse prognosis, hospitalization, permanent neurological deficits, death). Any serious adverse event occurring in the course of clinical research, in addition to timely active and effective treatment, the investigator should report the serious adverse event to the ethics committee of the research unit within 24 hours after learning about it. At the same time, the serious adverse event form must be filled in to record the occurrence time, severity, duration, measures taken and outcome of serious adverse events.

3. Medical safety measures If adverse events occur during the study, regardless of whether they are causally related to the intervention measures, the principal investigator should immediately give necessary and appropriate treatment and explain it to the study participants. At the same time, adverse events were followed up until they returned to normal or the principal investigator determined that no further follow-up was necessary. In addition, the principal investigator must record all adverse events in the case report form.

4. Communication with Ethics Committee and superior drug regulatory authorities Conduct clinical trials in accordance with the content of ethical approval, and timely communicate with ethics committee and superior drug regulatory authorities when there are problems encountered in the course of the trial or when the trial plan needs to be modified. Consent is required to change the test protocol. Communicate when there is a problem.

5. The entry and management of the internal data analysis plan shall be the responsibility of the designated data manager. In order to ensure the accuracy of the data, two data managers should independently make two copies of the input and proofread. For problems in the case report, the data manager will produce an answer sheet and send an inquiry to the investigator through the Clinical Ombudsman, who should answer and return as soon as possible. The data manager will modify, confirm and enter the data according to the researcher's answers.

Compliance with ethical principles and related regulations

This trial will be conducted in accordance with the research protocol, the Guidelines for the Ethical Review of Life Sciences and Medical Research Involving Humans (2023), the Guidelines for the Ethical Review of Biomedical Research Involving Humans (2016), the WMA Declaration of Helsinki (2013), and the CIOMS International Ethical Guidelines for Biomedical Research on Humans (2002). Health institutions conducting investigator-initiated Clinical Research Management Measures (Trial) and Ethical Principles of GCP research implement all applicable laws and regulations of the country. Conduct the study only after obtaining written approval from the Ethics Committee (IRB/IEC) on the protocol, informed consent, and study participant recruitment materials/processes. The proposed amendments also require IRB/IEC approval.

Statistical analysis plan

1. Analysis Set

(1) Full analysis Set (FAS) : All randomized study participants who were evaluated for efficacy at least once were deleted from the analysis set for data that were not evaluated for efficacy at least once.

(2) Meeting protocol set (PP) : Study participants in FAS who met the inclusion criteria and did not meet the exclusion criteria, completed the CRF form as planned, and did not use drugs that might affect the efficacy evaluation during the trial. Safety Dataset (SS) : Study participants who received at least one treatment after randomization.

2. Statistical Analysis

(1) The statistical analysis plan will be developed before the end of the trial and determined before the database is locked. Including statistical description and analysis methods, all statistical tests were carried out by bilateral test and SPSS22 was used for

statistics. For patient information, if it is a continuous variable and follows normal distribution, it is described by mean \pm standard deviation, and the difference between groups is compared by T-test. Those who did not follow the normal distribution were expressed as the median (upper and lower quartile), and the difference between groups was compared using the non-parametric rank sum test (Mann-WhitneyU test). For categorical variables such as the incidence of hypoxia, the frequency and rate (or composition ratio) were expressed, and the difference between groups was compared by Chi-square test or Fisher exact probability method.

(2) Main indicators:

- 1) Intraoperative hypoxia was described by frequency (incidence) and Chi-square test or Fisher analysis was intended to determine whether there was a difference in the incidence of hypoxia between the two groups. Test $P < 0.05$ was considered statistically significant, and confidence interval was 95%.
- 2) Processing of missing data: Missing data or illogical data delete cases with missing values or use missing value filling methods (mean interpolation, maximum likelihood estimation, or multiple interpolation, etc.).
- 3) It is planned to collect clinical data and CRF tables of all subjects for examination, data entry and statistical analysis before May 2025.

Description of the new oropharyngeal airway used in the test

This product is produced and sold by Shanghai Elifu Medical Technology Co., LTD., and has been officially put into clinical use in March 2023. The product is named oropharyngeal airway for disposable endoscope, which is composed of nasal plug, bite, oropharyngeal channel, oxygen supply tube, lanyard and optional accessories carbon dioxide gas catheter and carbon dioxide collection tube. The model used in this study is JK (Oropharyngeal airway for endoscope with end-expiratory carbon dioxide Collection) with L/M/S three specifications, which is used to prevent airway obstruction caused by backward tongue fall during endoscopic surgery/examination, establish oropharyngeal airway for patients, and provide nasal oxygen at the same time. Usage: 1) Put the bite into the patient's mouth and fix it behind the patient's head with an elastic lashing rope; 2) One end of the oxygen supply tube is connected to the oxygen delivery interface at the bite of the inlet pharynx vent, and the other end is connected to the center for oxygen supply and pre-oxygen delivery; 3) According to routine clinical procedures, the

patient was implanted into the oropharyngeal channel after anesthesia;4) When the JK/JK1 type is used, connect the carbon dioxide gas pipe with the carbon dioxide collection pipe, and connect the carbon dioxide collection pipe connection port to the carbon dioxide monitoring device;5) Endoscopic operation can be started;6) Patients were monitored with oxygen inhalation and end-expiratory carbon dioxide collection during endoscopic surgery or examination. This product should be operated by professional personnel, and the medical personnel using this product should be trained in the corresponding technology.

How research results are published

The results of the study will be published in the form of a paper, and 1-2 articles included in SCI will be published.

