	Discharge rating scale scores more than 9 points, patients can be accompanied by relatives and friends. The incidence of hypoxia ($75\% \leq \text{SpO}_2 < 90\%$, $\leq 60\text{s}$) and severe hypoxia ($\text{SpO}_2 < 75\%$ or $75\% \leq \text{SpO}_2 < 90\%$, $\geq 60\text{s}$) during anesthesia were recorded. The incidence of choking, reflux aspiration and laryngeal spasm were recorded. The time of intervention was half or disappearance of end-expiratory carbon dioxide and/or disappearance of thoracic fluctuation and/or $\text{SpO}_2 < 95\%$, that is, open airway manipulation was taken successively until $\text{SpO}_2 \geq 95\%$, and the last means of opening the airway was recorded. The means of opening the airway of the two groups were the same, including: 1) adjusting the oxygen flow; 2) Lift the lower jaw; 3) Mask ventilation (pull out the gastroscope if necessary); 4) Tracheal intubation or laryngeal mask for ventilator assisted ventilation.
Shedding/culling criteria	After postoperative recovery, patients were assessed for adverse reactions. The score of discharge scale after sedation/anesthesia was more than 9 points. Patients could be accompanied by relatives and friends to leave the hospital.
Shedding/culling criteria	Patients who were lost to follow-up, had adverse events, or voluntarily withdrew from the trial
Early exit criteria	Patients with severe airway spasm, obstruction of ventilation, inability to effectively improve airway, and need emergency tracheal intubation or cricothyroid puncture.
Primary outcome measure	Incidence of hypoxia ($75\% \leq \text{SpO}_2 < 90\%$, $\leq 60\text{s}$) during anesthesia and sedation.
Secondary outcome measure	1, severe hypoxia ($\text{SpO}_2 < 75\%$ or $75\% \leq \text{SpO}_2 < 90\%$, $\geq 60\text{s}$) 2, the incidence of airway intervention 3, intraoperative dose of additional drugs 4, endoscopist satisfaction 5, recorded adverse events: choking, laryngeal spasm and reflux aspiration incidence; Apnea or slow breathing episodes (defined as respiratory rate ≤ 6 beats/min); Bradycardia is defined as a heart rate ≤ 50 beats/min. Serious adverse events such as tracheal intubation, non-invasive ventilation, use of vasopressors, and hospitalization are required.

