
must be avoided and conscious intubation under surface anesthesia or guided intubation under fiberoptic bronchoscope should be adopted [4]. To sum up, airway management in obese patients is a clinical focus and difficulty. In order to reduce the trauma of patients and promote ERAS, endotracheal intubation is often not possible during the operation of painless gastroenteroscopy. Therefore, it is a topic worthy of our exploration to not only meet the comfort requirements of patients, but also ensure the safety of patients during the whole perioperative period. Whether the birth of new oropharyngeal airway can solve the ventilation problem of obese patients during anesthesia is the significance of this research.

【reference】

- [1] Zeng Shiying, ZHANG Longyu, ZHAO Xinyuan, ZHANG Jin, BAI Junyun. Effect of nasal continuous positive airway pressure on patients with obstructive sleep apnea syndrome [J]. World Journal of Sleep Medicine, 2021, 8(03):537-538.
- [2] Pang Congyi, Yi Jingde. Effect of nasal continuous positive airway pressure on patients with chronic heart failure complicated with obstructive sleep apnea hypopnea syndrome [J]. Medical food therapy and health, 2021, 19(12):48-49.
- [3] Liu Xiaojie, Li Dajiang, Ning Jishun, et al. A case of severe hypoxemia in obese patients undergoing radical general anesthesia for colon cancer [J]. Journal of Clinical Anesthesiology, 2016, 32(05):518.
- [4] Hang Yannan. Handbook of Contemporary Anesthesia [M]. 2nd Ed. Beijing: World Book Publishing House, 2011: 358-363.

Research content:

1. Study population

The principal investigator was responsible for recruitment under strict control, and 130 patients with obstructive sleep apnea hypopnea syndrome (diagnosed as OSAHS by polysomnography monitoring) who underwent painless gastrocolonoscopy from today were selected. They were informed and consented to this clinical trial.

2. Sample size calculation:

According to the pre-test results, the incidence of hypoxia in the test group and the control group were 0.2 and 0.5, respectively. The sample size was calculated using PASS software, and the bilateral test level $\alpha=0.05$ and the test efficacy power=0.9

were set. 52 cases were required in each group according to the incidence of hypoxia, and 65 cases in each group were calculated after considering 20% shedding rate, totaling 130 cases.

3. Specific research content:

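### The removal rules for withdrawal and loss to follow-up are not limited to patients without an outcome, so they conflict with the full analysis set, and the protocol does not say which governs the primary test

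*Protocol*

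**What the plan says.** Four parts of the protocol bear on this.

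- **Research Methods, 1.3 Exclusion/removal criteria.** Two grounds are listed: "1) The patient voluntarily withdrew the informed consent", and cancellation of the operation. No time limit is attached to the first.
- **Scheme summary, Shedding/culling criteria.** The list is wider: "Patients who were lost to follow-up, had adverse events, or voluntarily withdrew from the trial". Again nothing restricts it to patients whose outcome was not observed.
- **Statistical analysis plan, 1. Analysis Set.** The FAS is defined as "All randomized study participants who were evaluated for efficacy at least once", and only those never evaluated are taken out.
- **Research content, 2. Sample size calculation.** The requirement for hypoxia is raised for attrition: "65 cases in each group were calculated after considering 20% shedding rate, totaling 130 cases".

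The primary outcome is the incidence of hypoxia "during anesthesia and sedation". Consent is signed before induction, participants may withdraw at any time, and the trial is open (Research Methods, 3 and 5; Research program, 1). The main-indicator paragraph gives the test for hypoxia but no analysis set.

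**The concern.** For this endpoint a patient's possible exits fall into two groups. Before sedation nothing has been observed, so removal costs no outcome. After waking, the primary outcome is already complete. Loss to follow-up can occur only after the session, so it can affect only later items such as sore throat or patient satisfaction.

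A removal rule that ignores this distinction reaches patients whose primary outcome is on file. Dropping them costs precision. It also lets the analysed groups depend on what happened after randomisation, in a trial where everyone knows the allocation and only the test arm has the airway device. If the choice between the removal list and the FAS is left open, it may be made when results by arm are already visible.

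**Working it through.** **1. The plan's own figure.** Inputs from the sample size section: "the incidence of hypoxia in the test group and the control group were 0.2 and 0.5, respectively", with "the bilateral test level $\alpha=0.05$ and the test efficacy power=0.9". With a pooled variance under the null and no continuity correction, the mean rate is 0.35:

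n = [1.96 × √(2 × 0.35 × 0.65) + 1.2816 × √(0.2 × 0.8 + 0.5 × 0.5)]² / 0.3²
= [1.322 + 0.821]² / 0.09 = 51.01, rounded up to 52.

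This agrees with "52 cases were required in each group according to the incidence of hypoxia". Attrition: 52 / (1 − 0.20) = 65 per arm, 130 in total. Both stated figures reproduce. The allowance is 65 − 52 = 13 per arm, or 26 overall.

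**2. The rules side by side.**

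| Patient | 1.3 | Summary | FAS |
|---|---|---|---|
| Operation cancelled, or consent withdrawn, before anaesthesia | removed | shed if withdrawn | out (never evaluated) |
| Treated, consent withdrawn after waking | removed | shed | in |
| Treated, lost after the session | not mentioned | shed | in |

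The first row is consistent. The second and third are not, and those are the patients with an observed primary outcome.

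**3. Ceiling on the loss of precision.** Assume every one of the 13 per arm could have been kept.

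Power = Φ{[0.3√n − 1.322] / √0.41}
- n = 52: Φ(1.314) = 0.906
- n = 65: Φ(1.713) = 0.957

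95% CI half-width = 1.96 × √(0.41 / n)
- n = 52: 0.174
- n = 65: 0.156

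**4. Selection, by assumption only.** The documents give no withdrawal rates by outcome or arm. Suppose 20% of hypoxic and 5% of non-hypoxic patients leave after waking.

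- Test arm: 0.2 × 0.80 / (0.2 × 0.80 + 0.8 × 0.95) = 0.16 / 0.92 = 17.4%, against a true 20%. With 30% of hypoxic patients leaving, 0.14 / 0.90 = 15.6%.
- Control arm, if the 20% and 5% also apply there: 0.5 × 0.80 / (0.5 × 0.80 + 0.5 × 0.95) = 0.40 / 0.875 = 45.7%.
- Losses in the test arm only: difference 50 − 17.4 = 32.6 points instead of 30. The same losses in both arms: 45.7 − 17.4 = 28.3 points.

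So the direction depends on whether the losses differ between arms.

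**5. Effect on false positives, again by assumption.** With no true difference, 65 per arm, and hypoxic patients removed from the test arm only (40,000 simulated trials, Pearson chi-square without correction):

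| Share of hypoxic test-arm patients removed | Rejection rate, true rate 0.50 | Rejection rate, true rate 0.35 |
|---|---|---|
| 0% | 4.5% | 5.3% |
| 20% | 9.5% | 8.9% |
| 30% | 16% | 15% |

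**The case against.** The strongest reply is that the FAS is the only text defining who is analysed, and it keeps these patients. On that view the removal lists govern participation, and item 1 of 1.3, which stands beside cancelled operations, can sensibly mean withdrawal before induction. A separate analysis plan, due before database lock, could settle the rest.

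Much of this stands. A reader might infer that observed outcomes will be thrown away. The documents do not establish that, because the FAS as written retains them. A reader might also infer that 26 patients are expected to be lost from an endpoint that such losses cannot make missing. That is unsupported too: the 20% is not broken down and may include cancellations, withdrawals before induction, adverse events and the automatic withdrawals after airway emergencies in the termination procedures. Even at 52 per arm, power meets the stated 0.90.

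The bias illustration is also limited. It ties withdrawal to hypoxia, whereas the likelier motives are throat discomfort or a difficult procedure. Withdrawal unrelated to hypoxia would not bias the hypoxia rate.

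The reply does not remove the conflict. The lists, the FAS and the shedding rate are all fixed in this protocol. Raising the hypoxia sample size for shedding makes sense only if shed patients do not count towards the 52. The missing-data paragraph also permits deleting cases with missing values, which could reach a treated patient who lacks only a later item.

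**Conclusion.** The point holds as an unreconciled conflict, not as demonstrated data loss or bias. For a treated patient who withdraws or is lost after the session, the removal criteria and the FAS give opposite answers, and the protocol names neither the governing rule nor the analysis set for the primary test.

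If the removal lists were followed, observed primary outcomes would be discarded after they are known, with possible selection by arm or by experience of the procedure. The precision at stake is at most the gap between 52 and 65 per arm shown above, and it reaches that only if all of the shedding is avoidable. The bias figures rest on assumed withdrawal rates and show only that one-sided losses could matter.

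This conclusion covers withdrawal and loss to follow-up. Shedding for adverse events, and automatic withdrawal after airway emergencies, are more directly tied to hypoxia and need the same reconciliation with the FAS.

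**What to change.** In 1.3 and in the summary's shedding row, limit removal from analysis to patients who withdraw or are cancelled before anaesthesia starts, since they have no outcome. Then state that:

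- later withdrawal or loss ends further data collection only;
- outcomes already recorded (hypoxia, severe hypoxia, airway intervention, events during the procedure) are analysed as randomised in the FAS and safety set, unless the patient withdraws permission to use the data;
- only items due after the withdrawal or loss are treated as missing;
- the FAS is the primary analysis set.

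Confirm that the consent form carries matching wording, or add it; the consent pages are not in the copy reviewed, so it may already be there.

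The cost is a few sentences and a protocol amendment, which the ethics section says needs IRB/IEC approval. No study procedure or sample size changes.
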